BACKGROUND: Hemiparesis, spasticity and reduced motor control are typical impairments after stroke and commonly contribute to motor deficits that affect gait. These deficits manifest as reduced velocity, decreased cadence and asymmetries in temporal, spatial and force parameters during ambulation. Robotic-based therapies have been used to increase gait velocity and reduce asymmetry in a population of individuals after stroke, however these therapies have demonstrated results similar to that of conventional training. This is possibly due to guided-assist control strategies used to deliver robotic training, which strategies limit participant involvement and thus constrain motor learning.

The TPAD is a robotic device that employs actuated tethers at the user's pelvis to guide the user's pelvis along a pre-set movement trajectory. The TPAD tethers can be configured in an infinite array of possibilities, and most recently have been used to increase loading onto the paretic limb in a population of individuals after stroke. While other robotic devices guide the limb through the motor trajectory, and constrict the participants ability to participate in the motor planning and movement execution, the TPAD promotes weight shifting, but allows an individual to freely move the limb and to navigate spatiotemporal aspects of training independently. Further, if coupled with overground to focus on addressing a specific task goal, this device may prove useful to improve symmetry in individuals after stroke.

OBJECTIVES: The purpose of this study is to evaluate the overall feasibility in terms of safety, treatment tolerance and adherence as well as address preliminary efficacy of implementing a treatment paradigm using the TPAD with visual feedback and overground training to reduce load asymmetry on the treadmill and promote increased stance symmetry on the paretic limb during overground gait.

PARTICIPANTS: To account for 20% attrition, a total of 12 individuals in the chronic (>6 months) stages post stroke will be recruited from a voluntary stroke research registry with anticipation that 10 individuals will complete participation.

DESIGN: A non-randomized pilot study of feasibility will be used to establish the preliminary efficacy of using the TPAD in combination with overground training to reduce load force asymmetry in this population.

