Following these three visits of Pre-Test assessments, participants will return to complete five consecutive days of the training intervention. The intervention will consist of five consecutive days of TPAD training plus visual feedback training with a short over ground training (5-10 minutes) each day immediately following completion of treadmill based activities. After participants are readied for intervention, they will be assisted onto the treadmill and the treadmill will be initiated. Individuals will self-select gait speed with a physical therapist confirming speed is safe for the duration of training. Once gait speed is set, individuals will initiate five minutes of Baseline gait on the treadmill during which load force measures are recorded at minute 0-1 (BL1), minute 2-3 (BL2) and minute 4-5 (BL3). This Baseline gait will be followed by 40 minutes of tethered TPAD training with visual feedback provided. The amount visual feedback will be faded over the course of the five-day training. On completion of the tethered portion of training, participants will continue to ambulate on the treadmill for an additional 10 minutes during a Post-Training period. Measures of load force will be recorded during minute 0-1 (PT1), minute 3-4 (PT2), minute 6-7 (PT3) and minute 9-10 (PT4) of Post Training. Participants will then be assisted off the treadmill and an additional 5-10 minutes of over ground training will be conducted reinforcing weight shifting onto the paretic limb. Participants will be required to complete at least four days of training for data to be considered in the final analysis. Training sessions will last approximately 60 minutes (one hour) in duration.

On the fifth day of training, immediately following the final training session, participants will be allowed a 10-15 min seated rest break and over ground measures will be reassessed (Post

Test). All participants will be asked to return one week after completion of the intervention to undergo one final over ground assessment (Follow Up).

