### **Study Outcomes**

#### **1. Feasibility**

The primary feasibility outcomes will include an evaluation of safety, tolerance to treatment, and adherence over the course of the trial.

**1.1.** Safety of the intervention will be assessed by recording the number of adverse events (AE) and/or serious adverse events (SAE) that occur throughout the duration of the trial and will be reported as summary data.

**1.2** Treatment tolerance will be measured primarily by rates of perceived exertion (RPE) and secondarily by the percentage of maximum heart rate (HRmax) throughout daily training sessions.

**1.3** Rates of adherence will be presented as a proportion of visits attended out of the total study visits. Participants who are not able to complete at minimum four out of the five training visits (80% adherence) will not be included in the final data analysis.

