### **5. Missing Data**

Missing data will be identified as soon as possible after data collection and an attempt made to get as much information as possible about the data point in question.

Missing data will be excluded from the final analysis. If a single variable has more than 15% of data missing, this variable will not be included for interpretation in the final results.

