#### ***2.1.2 Treatment Tolerance***

Group means (SD) of Rate of Perceived Exertion (RPE) over the course of the intervention will be reported summararily for the group. A repeated measures analysis of variance (ANOVA) will be used to determine effect, or change of RPE over the course of the intervention (by day). The percentage of maximum heart rate (HRmax) will also be reported using descriptive measures (mean, standard deviation) for the group, and a repeated measures ANOVA used to assess for change over the course of the intervention.

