### ***2.2.2 Stance Time Symmetry Ratio***

Descriptive values (mean (SD)) of stance symmetry will be included in the final report. Mean values of Stance symmetry ratios will be analyzed using repeated measures ANOVA to first compare the relationship of the multiple pre-test measures. If there is no significant difference between the multiple pre-test measures, then the mean of the pre-test measures will be compared to measures at post-test and follow up also using a repeated measures ANOVA. Bonferonni corrections will be used to control for multiple comparisons. The F value and statistical significance will be reported with 95% confidence intervals and effect sizes. A graphical representation of the data will also be reported.

Secondarily, a linear regression model of daily change over time will be created using change scores from the mean of the three Pre Test measures to Day 1 of training. Within day changes for each of the five training days and changes from daily Pre Testing and from daily Post Testing will also be examined with a regression over time. Results of the regression models will be used to determine the presence of a significant change over the course of the intervention and will be reported with the corresponding slope.

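### Participants whom the plan retains with four of five training visits, or without a Follow Up, would fall out of its repeated measures ANOVAs; a mixed model would keep their data

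*SAP*

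**What the plan says.** **Who is kept.** The SAP text under Figure 1 states: "Participants will be required to complete at least four days of training for data to be considered in the final analysis". SAP Study Outcomes 1.3 repeats the rule from the other side: those "not able to complete at minimum four out of the five training visits (80% adherence) will not be included in the final data analysis". One missed training visit is therefore accepted. Protocol VII lists grounds on which a participant may be withdrawn: incomplete Pre-Tests, fewer than four of five training visits, no Post-Test, or a disabling injury. A missed Follow Up is not among them.

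**How change is tested.** SAP 2.1.2 uses a repeated measures ANOVA for "change of RPE over the course of the intervention (by day", and the same method for percentage of maximum heart rate across the intervention. For stance symmetry, SAP 2.2.2 says that "the mean of the pre-test measures will be compared to measures at post-test and follow up also using a repeated measures ANOVA". Sections 3.2 to 3.8 give the same three-level comparison for the secondary gait and balance outcomes.

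**Missing values.** SAP section 5 says: "Missing data will be excluded from the final analysis". It adds that a variable with more than 15% of its data missing will not be interpreted. It names no imputation and no model for incomplete records.

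**The concern.** The rule for entering the analysis tolerates gaps that the named test does not. A standard repeated measures ANOVA needs a value at every level of the within-person factor: five days for tolerance, three time points for gait and balance. A person with one gap is lost from that test, along with the values that were observed.

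Two kinds of absence matter, and they affect different tests. A missed training day affects the RPE and heart rate ANOVAs. A missed Follow Up affects the stance, gait and balance ANOVAs. The second is harder to justify for stance, because the primary question (SAP Specific Objectives, question 3, and Study Outcomes 2.2) runs from mean Pre-Test to Post-Test and does not need Follow Up.

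Tolerance is a primary feasibility outcome, and the SAP intends the results to inform the planning and size of later trials. With about ten people, losing a few from a test matters. The by-day trend would also describe only those who attended all five sessions.

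**Working it through.** **Inputs.** The protocol abstract gives the sample: "To account for 20% attrition, a total of 12 individuals", "with anticipation that 10 individuals will complete participation". Check: 12 × 0.80 = 9.6, or about 10. (Inflating 10 by 1/(1 − 0.20) gives 12.5, so 13; the difference does not matter here.) There is no power calculation. I take n = 10 retained. The documents give no rate of missed visits, so the per-visit probability p is an assumption: 2%, 5% or 10%, independent across visits.

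**Share of retained participants who leave the by-day tests.** Retained means at least four of five visits.

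- P(five visits) = (1 − p)^5; P(exactly four) = 5p(1 − p)^4
- Share of the retained with exactly four = 5p / (1 + 4p)

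| p (assumed) | Share with four days | Expected left of 10 | P(at least one of 10 lost) |
|---|---|---|---|
| 2% | 0.10/1.08 = 9% | 9.1 | 62% |
| 5% | 0.25/1.20 = 21% | 7.9 | 90% |
| 10% | 0.50/1.40 = 36% | 6.4 | 99% |

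The Post-Test follows training on Day 5, so a person absent that day may also lack a Post-Test and may be withdrawn under Protocol VII. If all such people are removed, the share becomes 4p / (1 + 3p): 0.08/1.06 = 8%, 0.20/1.15 = 17%, 0.40/1.30 = 31%. The picture is the same.

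**What is lost.** If two of ten each miss one day, observed person-days are 8 × 5 + 2 × 4 = 48. The ANOVA drops 8 of them (17%).

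If three of ten each miss one day, the ANOVA keeps 7 people, with (7 − 1) × 4 = 24 error degrees of freedom. A participant-plus-day model on all observed values keeps 10 people and 47 person-days, with 47 − 10 − 4 = 33.

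**Illustrative power.** A simulation of that three-of-ten case (2,000 runs) assumed a linear RPE rise of 2 points over five days, a within-person SD of 1.5, and the missed day chosen at random. Power was 0.50 for the ANOVA on complete participants, 0.66 with all observed days, and 0.71 with nothing missing. For a 1.5-point rise the figures were 0.30, 0.41 and 0.43. The all-days analysis fitted participant and day as fixed effects. It shows the value of the retained data and is not a test of the mixed model proposed below.

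**Follow Up.** With ten people and three time points, error degrees of freedom are 9 × 2 = 18. One missed Follow Up reduces this to 8 × 2 = 16 and removes one of ten complete Pre-Post pairs from the ANOVA.

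**Does the 15% rule prevent this?** Not reliably, because its denominator is not stated. Two single missed days are 2/50 = 4% of person-days but 2/10 = 20% of participants. Counted over person-days, seven people could each miss one day (7/50 = 14%) and RPE would still be interpreted, with three people in the ANOVA and 2 × 4 = 8 error degrees of freedom. One missed Follow Up is 1/30 = 3.3% of the three-level cells or 1/10 = 10% of Follow Up values, below 15% either way.

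**The case against.** The SAP never says complete-case or listwise. Excluding missing data could mean dropping only the missing values, and a repeated measures ANOVA can be fitted as a participant-plus-day linear model on unbalanced rows. The four-of-five rule is a floor for entering the analysis and does not promise that everyone enters every test. Much of the data would still be used: group means of RPE and heart rate, reported adherence, and the daily regressions. Bonferroni-corrected comparisons in 2.2.2 could keep each Pre-Post pair if run as separate paired tests. The miss rates are assumed. The trial is a single-arm pilot with no power target and no tolerance threshold tied to the ANOVA, so a sentence on handling incomplete participants might suffice.

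Much of this stands. A reader might infer that the SAP prescribes complete-case analysis, or that its retention and analysis rules contradict each other. The documents support neither: the loss is a consequence of the named method in its standard form. A reader might also infer that partial records are wasted throughout; they are lost only to the ANOVA tests. What remains is that the SAP names a method which ordinarily cannot use these participants, and states no alternative.

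The most tempting inference is that losing absentees pushes the exertion trend toward no change and makes tolerance look better. That is possible, since Protocol X foresees severe fatigue that halts procedures. But the documents give no reasons for missed visits and no RPE trend, and absence may be logistical.

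**Conclusion.** The point holds as a limited one and should be fixed, though it does not threaten the trial. Run in the standard way, the by-day tolerance tests would include only people who attended all five training sessions, and the stance, gait and balance ANOVAs only people with a Follow Up. Under assumed independent miss rates of 2% to 10% per visit, about 1 to 4 of 10 retained participants would leave the tolerance tests. Each missed Follow Up would remove one person from the other ANOVAs. With perfect attendance nothing is lost. The effect on precision follows from the numbers above. Bias is possible if absence is related to exertion, but its direction and size cannot be derived from the documents. The 15% rule is not a dependable safeguard.

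**What to change.** In SAP 2.1.2, 2.2.2 and 3.2 to 3.8, replace the repeated measures ANOVA across days or across Pre/Post/Follow Up with a linear mixed model: day or visit as a fixed factor, participant as a random effect, REML with Kenward-Roger degrees of freedom, and all observed values used. For stance symmetry, take the Pre-to-Post contrast from that model as the answer to the primary question. Report the number of participants contributing to each test.

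The cost is SAP wording and standard software; no new data or participants are needed. With complete, balanced data the model reproduces the ANOVA under compound symmetry, provided the variance estimate is not negative.

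The limits should be stated. The model assumes missing at random and, with a random intercept, compound symmetry. It does not repair absence driven by unobserved intolerance, and it does not reach people excluded for completing fewer than four visits.

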#### ***2.1.3 Adherence***

The proportion of adherence to the intervention will be reported descriptively as a percentage of total visits.

### **2.2 Primary Outcomes of Preliminary Efficacy**

Prior to statistical analysis, a visual inspection of the data will be completed. Celeration lines with additional 2 standard deviation bands will be added to graphical representations of the data to aid in statistical analyses.

#### ***2.2.1 Load Force (Fz)***

Mean values of Fz Symmetry Ratios will be compared over the course of the five-day training. Specifically, after normality is tested, either a Wilcoxon Signed Ranks test or a paired t test will be used to examine ratio values from the mean of Baseline Day one

to Post Training Day 5. These values will be reported with the associated level of significance. Effect sizes and 95% confidence intervals will also be calculated and reported in the final report. Results will also be presented graphically.

### ***2.2.2 Stance Time Symmetry Ratio***

Descriptive values (mean (SD)) of stance symmetry will be included in the final report. Mean values of Stance symmetry ratios will be analyzed using repeated measures ANOVA to first compare the relationship of the multiple pre-test measures. If there is no significant difference between the multiple pre-test measures, then the mean of the pre-test measures will be compared to measures at post-test and follow up also using a repeated measures ANOVA. Bonferonni corrections will be used to control for multiple comparisons. The F value and statistical significance will be reported with 95% confidence intervals and effect sizes. A graphical representation of the data will also be reported.

Secondarily, a linear regression model of daily change over time will be created using change scores from the mean of the three Pre Test measures to Day 1 of training. Within day changes for each of the five training days and changes from daily Pre Testing and from daily Post Testing will also be examined with a regression over time. Results of the regression models will be used to determine the presence of a significant change over the course of the intervention and will be reported with the corresponding slope.

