### **SPECIFIC OBJECTIVES:**

1) Is this five-day intervention using the TPAD and incorporating faded visual feedback and overground walking feasible in terms of safety, treatment tolerance and adherence in individuals with chronic stroke who present with gait asymmetry?

As a measure of treatment efficacy, this study will specifically address the following questions:

2) Is this treatment paradigm effective at improving load force symmetry over the course of five training sessions as measured from Baseline Day one to Post Training Day five?

3) Is this training paradigm effective to promote transfer and improve stance time symmetry in over ground gait as measured from a mean of the three days in Pre Testing to Post Testing?

The presence of preliminary efficacy in the prior two questions, coupled with measures of safety, treatment tolerance and adherence will be used to answer the over arching question of feasibility and preliminary efficacy.

[figure not shown]

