**Figure 1: Trial Schema**

A total of 12 participants will be enrolled to participate. Participants will be assessed over a series of three over ground Pre-Tests by a member of the study team. On completion of over ground Pre Tests, symmetry ratios (paretic/non-paretic limb) will be calculated for percentage of time in stance phase. The mean value of these ratios will be calculated. As the minimal detectable change (MDC) for time in stance has been identified as 0.09, participants will be required to have a mean symmetry ratio of 0.90 or less of time in stance after Day one of Pre Testing to be considered eligible for participation in the trial. Details of other

inclusion/exclusion criteria can be found in the Standard Operating Procedure Manual for this study. The details of data collection are outlined here with an associated plan for statistical analysis.

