#### **2. Efficacy**

There will be two primary measures of preliminary efficacy. First, we aim to establish treatment efficacy on the treadmill. Additionally, we aim to determine whether individuals will

be able to transfer gains to improve symmetry in over ground parameters. Specific outcomes are as follows:

**2.1** The primary outcome measure for efficacy of training on the treadmill will be the calculated load force symmetry ratio as measured load force recorded during Baseline and Post Training on the treadmill with embedded force plates.

**2.2** The primary outcome measure for efficacy of transferability will be the stance symmetry ratio calculated from percentage of time in spent in stance phase of the gait cycle. This will be extracted from data provided by APDM® inertial sensors and measured by the mean of the Pre Test visits to Post Testing.

**2.3** Secondary measures of preliminary force efficacy will include within day changes in load force symmetry as taken on the treadmill. As secondary outcomes to evaluate for transfer of the intervention to overground gait, APDM® inertial sensors will be used to record the percentage of time spent in double support, time in swing phase, stride length, and stride velocity. Symmetry ratios will be calculated for percentage of time in swing phase of the gait cycle, and stride length. Gait velocity as a measure of time performing the 10MWT will also be recorded. Lastly, as an additional balance measure, we will also use the total score of the Berg Balance Scale (BBS).

See Table 1 for a detailed list of measures recorded.

Table 1. All outcome variables and time points at which they will be measured.

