### ***3.2 Swing Symmetry Ratio***

Descriptive statistics (Mean (SD)) will be calculated and reported. Mean values of swing symmetry will be analyzed using repeated measures analysis of variance (ANOVA) to compare the mean of the pre-test measures to measures at post-test and follow up. Bonferonni corrections will be used to control for multiple comparisons. Effect sizes, and 95% confidence intervals will be calculated and reported with the F/Z statistic and p value. A graphical representation of the data will also be reported. Similar to stance symmetry, a linear regression model of daily change over time will be created using change scores from the mean of the three Pre Test measures to Day 1 of training. Within day changes for each of the five training days and changes from daily Pre Testing and from daily Post Testing will also be examined with a regression over time. Results of the regression models will be used to determine the presence of a significant change over the course of the intervention and will be reported with the corresponding slope.

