### ***3.7 Gait Velocity***

Descriptive statistics (Mean (SD)) will be calculated and reported. Mean values of Stride Length Symmetry ratios will be analyzed using repeated measures analysis of variance (ANOVA) to compare to compare the mean of the pre-test measures to measures at post-test and follow up. Bonferonni corrections will be used to control for multiple comparisons. Effect sizes, and 95% confidence intervals will be calculated and reported with the F/Z statistic and p value. A graphical representation of the data will also be reported. Similar to stance and swing symmetry and double limb support, a linear regression model of daily change over time will be created using change scores from the mean of the three Pre Test measures to Day 1 of training. Within day changes for each of the five training days and changes from daily Pre Testing and from daily Post Testing will also be examined with a regression over time. Results of the regression models will be used to determine the presence of a significant change over the course of the intervention and will be reported with the corresponding slope.

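### SAP 2.2.2 runs the primary stance-symmetry test only if the three pre-tests do not differ significantly, and gives no step if they do

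*SAP*

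**What the plan says.** SAP Specific Objectives, question 3, asks whether training improves overground stance symmetry "as measured from a mean of the three days in Pre Testing to Post Testing". Study Outcomes 2.2 makes this the primary transfer outcome, "measured by the mean of the Pre Test visits to Post Testing". Neither sets a condition.

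Statistical Analyses 2.2.2 then sets one. A repeated measures ANOVA compares the three pre-tests, and: "If there is no significant difference between the multiple pre-test measures, then the mean of the pre-test measures will be compared to measures at". That comparison, with Post Test and Follow Up, is a further repeated measures ANOVA with Bonferroni correction. The opening of Statistical Analyses sets significance at p of 0.05 or lower for every analysis, so the same level applies to the gate. Neither 2.2.2 nor any other part of the SAP says what happens if the pre-tests differ. Protocol XI only refers to the SAP.

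Three things do not depend on the gate:
- the mean (SD) of stance symmetry;
- the graphs described at the start of Statistical Analyses 2.2: "Celeration lines with additional 2 standard deviation bands will be added to graphical representations of the data to aid in statistical analyses";
- the regressions in 2.2.2, introduced as secondary: "Secondarily, a linear regression model of daily change over time will be created using change scores from the mean of the three Pre Test".

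The parallel secondary analyses have no gate. SAP 3.2, for example, reads "Mean values of swing symmetry will be analyzed using repeated measures analysis of variance (ANOVA) to compare the mean of the pre-test measures to", again with Post Test and Follow Up as comparators, and 3.3 to 3.6 follow the same pattern.

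**The concern.** A primary outcome has a weaker guarantee of being tested than swing symmetry or stride length. If the pre-test ANOVA is significant, the analyst must either leave question 3 without its primary test or choose a replacement after seeing the data. The SAP uses the answers to questions 2 and 3, together with the feasibility measures, to judge overall feasibility and preliminary efficacy, so a gap in question 3 carries through.

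The gate also invites a wrong reading when it is passed. With about 10 people, a non-significant pre-test ANOVA is weak evidence that the baseline was stable.

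**Working it through.** The plan gives no error rate or power for the gate, so there is no figure to reproduce. The main check is of the text.

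**1. Text**

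| Place | Contrast | Condition |
|---|---|---|
| Specific Objectives, question 3 | pre-test mean to Post Test | none |
| Study Outcomes 2.2 | pre-test mean to Post Test | none |
| Statistical Analyses 2.2.2 | pre-test mean, Post Test, Follow Up | pre-test ANOVA not significant; no other branch |
| Statistical Analyses 3.2 to 3.6 | pre-test mean, Post Test, Follow Up | none |

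**2. Inputs for size**
- n = 10 completers (Protocol, Participants) and three pre-tests (SAP Study Design).
- Minimal detectable change 0.09 (SAP, text at Figure 1). Its confidence level is not stated.
- Read as a 95% value, SEM = 0.09/(1.96 × √2) = 0.0325. Read as a 90% value, SEM = 0.09/(1.645 × √2) = 0.0387.
- Drift d from Day 1 to Day 3, taken as linear and upward. All values of d are assumptions.

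**3. Chance that the gate closes.** The test is F with 2 and 18 degrees of freedom and critical value 3.55. With pre-test means at 0, d/2 and d, the noncentrality is λ = 10 × 2 × (d/2)²/SEM².

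| d | λ (SEM 0.0325) | Lost, 95% reading | Lost, 90% reading |
|---|---|---|---|
| 0 | 0 | 5.0% | 5.0% |
| 0.02 | 1.90 | 18.9% | 14.5% |
| 0.03 | 4.27 | 38.0% | 27.8% |
| 0.04 | 7.59 | 61.4% | 46.2% |

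Simulation of 100,000 trials (95% reading) gives 5.0%, 18.8%, 38.0% and 61.5%. At d = 0.02 the gate is passed in 100 − 18.9 = 81.1% of trials.

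**4. False positives if the pre-tests rise and then plateau, with no training effect.** The pre-test mean is d/2 and Post Test is d, so the bias is d/2 = 0.010, 0.015 and 0.020. The standard error of Post minus pre-test mean is 0.0325 × √(1 + 1/3)/√10 = 0.0119. Testing that pair at 0.05/3 (Bonferroni over three pairs) by noncentral t with 9 degrees of freedom, and simulating the three-level omnibus ANOVA, gives:

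| d | Bonferroni pair, ungated | Run and significant with gate | Omnibus, ungated | Run and significant with gate |
|---|---|---|---|---|
| 0.02 | 4.8% | 3.9% | 10.4% | 8.5% |
| 0.03 | 9.4% | 5.8% | 18.2% | 11.3% |
| 0.04 | 16.8% | 6.5% | 30.0% | 11.5% |

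**5. Error among trials that pass.** This comparison uses the uncorrected pair, only to show the pattern. If everyone drifts alike, error given a pass is 12.0%, 20.6% and 32.4%, against 11.8%, 20.5% and 32.6% ungated, which is the same within simulation error. If drift varies between participants (assumed SD 0.04), it is 8.8%, 13.5% and 20.4% against 10.2%, 16.8% and 26.6%.

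**6. Day 3 as baseline.** Under plateau drift the bias is d − d = 0, and simulated error stays near 5%. The standard error ratio to the three-day mean is √2/√(4/3) = 1.22. If the ratio instead rises by d again by Post Test, uncorrected Day 3 error is 24%, 46% and 69%, against 62%, 92% and 99% for the three-day mean.

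**The case against.** The strongest case on the other side is that the consequence is limited. This is a single-arm pilot meant to inform the size of later trials. A reader might infer that stance goes unanalysed when the gate closes, and the documents do not support that. The mean (SD), the graphs and the ungated regressions remain, and the regressions are meant to detect change over the intervention. This objection stands as a limit. But those regressions are labelled secondary and do not test the pre-test mean against Post Test.

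A reader might also infer that the gate gives no protection at all against drift. That holds only if every participant drifts alike. With drift that varies, error among passing trials falls somewhat, so the gate gives partial protection. It also lowers the total count of false positives, though mainly by leaving more trials without a primary result.

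Third, uncorrected paired tests would suggest false-positive rates of 12%, 21% and 33%. The SAP specifies Bonferroni correction, and on that basis the rates are 5%, 9% and 17%. A drift of 0.02 then does not push the pairwise result above 5%, although the omnibus test still reaches about 10%.

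Finally, every figure above the 5% baseline loss rests on a drift that the documents do not give. All were modelled upward, and a downward drift would reverse the bias.

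**Conclusion.** The point holds on the text. SAP 2.2.2 conditions the primary stance test and supplies no alternative, which departs from the SAP's own unconditional definition of the outcome and from its handling of the secondary outcomes. The intended contrast is clear. What is missing is what to do after a significant pre-test ANOVA.

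The 5% loss with stable pre-tests follows from the gate's own significance level. The larger losses assume 10 completers, linear drift and an error SD scaled from the 0.09 figure: 19% to 61% for drifts of 0.02 to 0.04, or 14% to 46% on the 90% reading. The gate gives at most partial protection, and passing it does not establish a stable baseline. The plan should be changed before analysis, but the flaw does not leave stance symmetry without any analysis.

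**What to change.** 1. Make the pre-test mean, Post Test and Follow Up ANOVA for stance symmetry unconditional, in line with Specific Objectives question 3 and Study Outcomes 2.2.
2. Report the three pre-test means with confidence intervals as a description of baseline stability, not as a gate.
3. Pre-specify one sensitivity analysis, always reported, with the last pre-test (Day 3) as baseline.

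The cost is SAP wording and one extra analysis of data already collected. It is not free of statistical cost. Under upward plateau drift the ungated test gives more false positives in total than the gated one (about 5%, 9% and 17% against 4%, 6% and 6 to 7% for the Bonferroni pair). That is why the Day 3 result belongs beside it.

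Day 3 should inform interpretation and not become a second hurdle. With stable pre-tests, requiring both results would cut power from about 78% to 71% for a true change of 0.045, and from about 39% to 31% for 0.03. The report should also say that the Day 3 analysis has a standard error about 22% larger and does not cure drift that continues to Post Test.
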